2 LIST OF ABBREVIATIONS AND DEFINITIONS OF TERMS

ACE	angiotensin converting enzyme
ADME	absorption/distribution/metabolism/excretion
AE	adverse event
ALT	alanine transaminase
ANC	absolute neutrophil count
ASCO	American Society of Clinical Oncology
AST	aspartate transaminase
AUC	area under the curve
AUC ₀₋₂₄	area under the curve from time zero to 24 hours
AUC _{0-t}	area under the curve from time zero to time t
BMT	bone marrow transplant
BP	blood pressure
BUN	blood urea nitrogen
C1D1	Cycle 1, Day 1
CAP	College of American Pathologists
CBR	clinical benefit rate
CFR	Code of Federal Regulations
CGH	comparative genomic hybridization
CISH	chromogenic in-situ hybridization
Cl/F	total plasma clearance
C _{max}	maximum concentration
CNS	central nervous system
CR	complete response
CRO	contract research organization
CT	computed tomography
CTC	circulating tumor cell
CTCAE	Common Terminology Criteria for Adverse Events (Version 4.03)
ctDNA	circulating tumor DNA
CYP	cytochrome P450
DBP	diastolic blood pressure
DCR	disease control rate
DLT	dose-limiting toxicity
DMC	Data Monitoring Committee
DNA	deoxyribonucleic acid
DR	duration of response
ECG	electrocardiogram
ECHO	echocardiogram
ECOG	Eastern Cooperative Oncology Group
eCRF	electronic case report form

EDC	electronic data capture
ER+	estrogen receptor positive
FACT-B	Functional Assessment of Cancer Therapy-Breast
FDA	Food and Drug Administration
FFPE	Formalin-fixed paraffin-embedded
FGF	fibroblast growth factor
FGFR	fibroblast growth factor receptors
FISH	fluorescence in-situ hybridization
GCP	Good Clinical Practice
GI	gastrointestinal
HDPE	high-density polyethylene
HER2	human epidermal growth factor receptor 2
hERG	human ether-a-go-go-related gene
HF	heart failure
HIPAA	Health Information Portability and Accountability Act
HLP	hemolymphopoietic
IB	investigator's brochure
IC ₅₀	Concentration of inhibitor required for 50% inhibition
ICF	Informed Consent Form
ICH	International Conference on Harmonization
IDMC	Independent Data and Monitoring Committee
IEC	Independent Ethics Committee
IHC	immunohistochemistry
IRB	Institutional Review Board
ITT	Intent to treat
IWRS	Interactive Web Response System
LFT	liver function test
LVEF	left ventricular ejection fraction
MDRD	Modification of Diet in Renal Disease
MRI	magnetic resonance imaging
msec	millisecond
MTD	maximum tolerated dose
MUGA	multiple-gated acquisition
NCI	National Cancer Institute
NE	Not evaluable
NGS	Next Generation Sequencing
NOAEL	no-observed-adverse-effect level
NSCLC	non-small cell lung carcinoma
ORR	objective response rate
OS	overall survival

PD	progressive disease pharmacodynamic
PDGF	platelet-derived growth factor
PDGFR α/β	platelet-derived growth factor receptors alpha and beta
PET	positron emission tomography
PFS	progression free survival
PK	pharmacokinetic(s)
POPPK	population pharmacokinetics
PR	partial response
PRES	Posterior Reversible Encephalopathy Syndrome
PRO	patient-reported outcomes
PT	prothrombin time
PTT	partial thromboplastin time
QoL	quality of life
qPCR	quantitative polymerase chain reaction
QT _c F	QT interval corrected using Fridericia's method
RECIST	Response Evaluation Criteria in Solid Tumors, Version 1.1
RNA	ribonucleic acid
RP2D	recommended Phase 2 dose
SAE	serious adverse event
SAS	statistical analysis software
SBP	systolic blood pressure
SD	stable disease
SOP	standard operating procedure
β -hCG	human chorionic gonadotropin β
SUSAR	suspected unexpected serious adverse reaction
$t_{1/2}$	elimination half-life
T3	triiodothyronine
T4	thyroxine
TMA	thrombotic microangiopathy
t_{max}	time to maximum concentration
TSH	thyroid stimulating hormone
UGT	uridine diphosphate-glucuronyltransferase
ULN	upper limit of normal
US	United States
VEGF	vascular endothelial growth factor
VEGFR	vascular endothelial growth factor receptors
V_{ss}/F	Volume of distribution at steady state
WBC	white blood cell

3 INTRODUCTION

3.1 Current standard of care for metastatic breast cancer

Metastatic breast cancer remains an incurable disease, with approximately 41,000 disease-associated deaths in the United States (US) annually [1]. Breast cancer includes three main molecular classes; i.e., estrogen receptor positive (ER+)/human epidermal growth factor receptor 2 (HER2)-negative breast cancers, HER2-overexpressing breast cancer, and triple negative breast cancers. ER+/HER2-negative phenotype is the most frequent and accounts for around 70% of all breast cancers. Endocrine therapy is the cornerstone treatment of ER+/HER2- metastatic breast cancer [2]. However, most of the patients will relapse after several months of treatment. Once endocrine resistant, prognosis is poor and patients with ER+/HER2- metastatic breast cancer are offered chemotherapy. For patients with HER2-overexpressing breast cancer, several therapies have been approved that meaningfully prolong progression free survival (PFS) and overall survival (OS) in these patients. With newer agents and combinations of existing agents, HER2-overexpressing breast cancer patients are experiencing profound and durable responses that can provide years of benefit. Lastly, those patients with triple negative breast cancer do not tend to respond to endocrine therapy or HER2-directed therapy. Therefore, these patients are generally offered chemotherapy with little hope for significant benefit. Although these three subtypes of metastatic breast cancer are treated with different drugs and have distinct prognoses, all of these patients will eventually develop resistance or intolerance to approved drugs. Therefore, there is a medical need for new pharmacological agents that improve outcomes for all patients with metastatic breast cancer.

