
Statistical Procedures
	
Analysis Populations
 
 • Efficacy population: all treated patients who received at least one dose of lucitanib and are confirmed as FGFR1- or 11q-amplified per the central laboratory • Safety population: all patients who have received at least one dose of lucitanib 
Sample Size Justification
 
Approximately 200 patients will be enrolled to the 10 mg and 15 mg daily dosing groups. A total of at least 80 patients in the 10 mg arm is sufficient to reliably estimate the median PFS and 6 month PFS rate in these heavily pre-treated patients. An observed median PFS greater than 4 months or similarly a 6-month PFS rate of at least 40% will be sufficient to consider the 10 mg dose group worthy of further study. Therefore, with at least 80 patients treated at 10 mg, the width of the 90% confidence interval for the 6 month PFS rate will be less than $\pm 10\%$ so that if the observed 6 month rate is 50% then the lower limit on the confidence interval will be greater than 40%.
 
Cohort C will enroll up to 40 patients to evaluate whether the PFS of a FGF non-amplified population is comparable to patients who are FGFR1- or 11q-amplified (Cohorts A and B).
 
The same target response of 40% will be used to evaluate Cohort C. With 40 patients, the width of the 90% confidence interval for the 6 month PFS rate will be less than $\pm 15\%$, so that if the observed 6 month rate is less than 25% then the upper limit on the confidence interval will be less than 40%, which is evidence that subsequent studies of 10 mg should exclude FGF non-amplified patients.
 
Statistical Methods
 
The Kaplan-Meier methodology will be used to summarize the primary endpoint of PFS. The 25th, 50th (median), and 75th percentiles will be presented along with the Kaplan-Meier estimates of the 6 and 12 month PFS rates.
 
The ORR and DCR will be summarized with frequencies and percentages. The DR and OS will be summarized utilizing Kaplan-Meier methodology.

Data Monitoring Committee
	
A data monitoring committee (DMC) consisting of two external investigator advisors and specified Clovis personnel will meet approximately quarterly after the first patient is enrolled to review the efficacy and safety data.
 
A detailed description of the composition, roles and responsibilities, and functioning of the DMC is provided in the DMC Charter.

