6 STUDY POPULATION

6.1 Number of Patients and Sites

FGFR1-amplified and 11q-amplified patients will be enrolled* as follows:

- Cohort A (10 mg): approximately 80 patients

FGF non- amplified patients will be enrolled into Cohort C as follows:

- Cohort C (10 mg): up to 40 patients

*1:1 randomization to Cohorts A and B was removed with Amendment #4.

Up to 20 patients will participate in a PK sub study to assess the comparative PK of the lucitanib tablet formulation with the lucitanib capsule formulation. Additional patients may be added to the PK sub-study to account for patients with incomplete PK sampling profiles at either Day -7 or Day 1, or to account for higher than expected variability in the observed PK profiles.

Enrollment into the PK sub study may only be opened at a limited number of sites based on study requirements and operational feasibility.

Patients in Cohorts A or C will be enrolled in the PK sub study at participating sites, as follows:

- Participation in the PK sub study will be optional for patients participating in Cohort A
- Participation in the PK sub study will be required for patients participating in Cohort C until enrollment of the PK sub study is completed

There will be approximately 30–40 investigative sites in the United States. All patients enrolled in Cohort C are required to participate in the PK sub study. Accrual to Cohort C will be limited to 10-15 sites participating in the PK sub study, until enrollment in the sub study has been filled.

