11.2 Statistical Methods

11.2.1 General Considerations

Patients randomized prior to implementation of Amendment #4 were stratified by FGF aberrancy (*FGFR1*- or 11q-amplified) and prior anti-angiogenic therapy (yes or no) status at baseline. Comparisons of the 15 mg and 10 mg dose groups may be stratified by these same factors. Patients that have amplification of both *FGFR1* and 11q are categorized as *FGFR1*-amplified for purposes of analysis. Since patients will no longer be randomized to the 15 mg dose group, the comparisons of the *FGFR1*-amplified, 11q-amplified, and FGF non-amplified subgroups will be made for the patients initially treated at 10 mg and for both dose groups.

Quantitative variables will be summarized using descriptive statistics (N, mean, standard deviation, median, minimum, and maximum) and/or frequency and percentages for medically relevant categories. Categorical variables will be presented using frequencies and percentages. Exact 95% confidence intervals may be presented for frequencies.

All data will be used to their maximum possible extent but without any imputations for missing data.

All statistical analyses will be conducted with the statistical analysis software (SAS[®]) system.

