## 8.2 **Baseline Clinical Characteristics**

Baseline characteristics variables to be summarized will include ECOG performance status, Hormone Receptor and Human Epidermal Growth Factor Receptor Status at diagnosis, location of metastatic disease, FGF status, breast cancer stage at diagnosis, number of prior anticancer therapies, number of prior adjuvant anticancer therapies, number of prior neoadjuvant anticancer therapies, and number of prior metastatic anticancer therapies, and time since diagnosis. Categorizations are provided below:

- ECOG: 0, 1, 2
- HR/HER2 Status at Diagnosis: HER 2-positive, ER-positive (and not HER 2-positive), PR-positive (and not HER 2-positive and not ER-positive), Triple Negative (note the hierarchical nature of these four categories)
- FGF status: 11q, FGFR1, FGFR1 & 11q, Negative
- Breast cancer stage: Occult, 0, I, IIA, IIB, IIIA, IIIB, IIIC, IV
- Number of prior metastatic anticancer therapies: <3, 3-6, >6
- Location of metastatic disease: bone only, visceral only, bone and visceral
- Time since diagnosis (months):  $\leq 12, >12-24, >24;$

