## **12** EFFICACY ANALYSIS

#### **12.1** Primary Efficacy Analysis

Kaplan-Meier methodology will be used to summarize the time to event variables including the estimated 50th (median) percentile by treatment group.

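### The PFS comparison by FGF status is not randomised and has no planned adjustment for tumour subtype or prior treatment, and the SAP leaves it out altogether

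*Protocol*

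**What the plan says.** **Prognosis.** Protocol 3.1, on ER-positive/HER2-negative, HER2-overexpressing and triple-negative disease, says that "these three subtypes of metastatic breast cancer are treated with different drugs and have distinct prognoses". Protocol 6.2 admits all three, requires at least first-line metastatic treatment and sets no upper limit on prior lines.

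**The comparison.** The protocol synopsis says "Cohort C will enroll up to 40 patients to evaluate whether the PFS of a FGF non-amplified population is comparable to patients" in Cohorts A and B. Protocol 11.2.1 adds that comparisons of the FGFR1-amplified, 11q-amplified "and FGF non-amplified subgroups will be made for the patients initially treated at 10 mg and for both dose groups".

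**The method.** Protocol 11.2.4.1 gives only Kaplan-Meier for PFS. The one mention of stratifying a comparison is optional and concerns dose: "Comparisons of the 15 mg and 10 mg dose groups may be stratified by these same factors". Those factors are FGF aberrancy and prior anti-angiogenic therapy.

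**The SAP.** SAP 12.1 says "Kaplan-Meier methodology will be used to summarize the time to event variables including the estimated 50th (median) percentile by treatment group". SAP 4 defines treatment group as initial dose (10 or 15 mg), whatever the cohort. SAP 8.2 lists "HR/HER2 Status at Diagnosis: HER 2-positive, ER-positive (and not HER 2-positive" and so on, plus number of prior metastatic therapies (<3, 3-6, >6), but only as baseline tabulations.

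**Recruitment.** Protocol 6.1 says "Accrual to Cohort C will be limited to 10-15 sites participating in the PK sub study, until enrollment in the sub study has been filled". The sub study takes up to 20 patients, and the trial uses about 30-40 sites.

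**The concern.** FGF groups are defined by tumour biology, so randomisation never balanced them, even when patients were randomised between 10 and 15 mg. If subtype or prior treatment differs between amplified and non-amplified patients, and also affects PFS, a crude comparison mixes that difference with any FGF effect. For a time, Cohort C also recruits from fewer sites, which is a second route to imbalance.

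The protocol promises the comparison but gives no method beyond Kaplan-Meier. The SAP does not carry it forward, and because it tabulates by starting dose, it does not plan even a check of baseline balance by FGF status. Any adjustment would then be chosen after open-label results were known.

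At stake is the biomarker conclusion: whether PFS on lucitanib differs by FGF amplification. The primary estimate of PFS in amplified patients is not in question.

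**Working it through.** **1. The plan's own precision figures.** Protocol 11.3 uses 90% intervals for the 6-month PFS rate. Half-width = 1.645 × √(p(1−p)/n), ignoring censoring.
- n = 80, p = 0.50: 9.2 points, lower limit 40.8% (plan: under 10 points, above 40%).
- n = 40, p = 0.25: 11.3 points, upper limit 36.3% (plan: under 15 points, below 40%).

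Both reproduce, but each describes one group alone. For the difference between 80 and 40 patients at 40% and 25%, the half-width is 1.645 × √(0.24/80 + 0.1875/40) = 14.4 points. The plan gives no precision or power for the difference.

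**2. Case mix with no FGF effect.** The documents give no PFS by subtype and no subtype shares by FGF status, so all inputs here are assumptions:
- exponential PFS, S(6) = exp(−ln 2 × 6 / median);
- median 5-6 months in non-triple-negative and 2-3 months in triple-negative disease;
- triple-negative share 10-15% in amplified and 25-40% in non-amplified patients.

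Spurious gap = (difference in shares) × (difference in S(6)).
- Smallest: medians 5 and 3, shares 15% and 25%: 0.10 × (0.435 − 0.250) = 1.9 points.
- Largest: medians 6 and 2, shares 10% and 40%: 0.30 × (0.500 − 0.125) = 11.3 points.
- Example: medians 5 and 2.5, shares 10% and 40%. Amplified 0.9 × 0.435 + 0.1 × 0.189 = 41.1%; non-amplified 0.6 × 0.435 + 0.4 × 0.189 = 33.7%; gap 7.4 points.

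SE in the example = √(0.411 × 0.589/80 + 0.337 × 0.663/40) = 9.3 points. The gap is 0.8 SE there, and 0.2 to 1.2 SE across the range.

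Swapping the two shares reverses the sign (33.7% against 41.1%), which would hide a real FGF effect. Nothing in the documents says which way the shares differ.

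A wider assumed range (amplified rate 40%, subtype spread 10-30 points, share difference 10-50 points) gives a gap of 1 to 15 points and an apparent hazard ratio of 1.03 to 1.51 under exponential PFS.

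**3. The Cohort C rule.** Protocol 11.3 treats an observed 6-month rate below 25% in 40 patients as evidence for excluding non-amplified patients. That means at most 9 of 40, ignoring censoring.
- True rate 40%: binomial probability 1.6%.
- Example, true rate 33.7%: 8.9%, against 1.1% if Cohort C had the amplified group's mix (41.1%).
- Lowest non-amplified rate in the first range (medians 5 and 2, share 40%): 0.6 × 0.435 + 0.4 × 0.125 = 31.1%, probability about 16%.
- Wider range: 2.1% to 44%.

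In the example, an observed rate equal to the true 33.7% has a 90% upper limit of 33.7 + 1.645 × √(0.337 × 0.663/40) × 100 = 46.0%, so the rule is not met.

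**The case against.** **Exclusion does not follow from the contrast.** A reader might infer that the FGF comparison decides whether later 10 mg studies exclude non-amplified patients. It does not. Protocol 11.3 and SAP 3 test Cohort C alone against a fixed 40%, so an adjusted hazard ratio would leave that rule unchanged. Nor does an example with the groups on either side of 40% show exclusion, since its upper limit is about 46%. This stands. What remains is that the Cohort C rate is itself open to case mix.

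**SAP 12.1 is not an unadjusted FGF comparison.** Its grouping is by starting dose. This also stands: the SAP omits the analysis, and the protocol leaves its method open. The exploratory endpoints do mention relating FISH cut-offs to clinical efficacy, but SAP 14 promises only descriptive summaries.

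**The prognostic statement is background.** The sentence in 3.1 goes on to say that all these patients eventually become resistant or intolerant. Protocol 6.2 requires relapsed or refractory disease, with HER2-directed options exhausted. The documents do not say that PFS differs by subtype in this later-line population. This weakens any claim about size, but not the case for checking.

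**Direction is unknown.** Protocol 3.2 links 11q amplification to poor prognosis, which could bias the other way and which subtype adjustment need not remove.

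**Site restriction is temporary.** The 10-15 site limit ends once the sub study of up to 20 is filled, while Cohort C may reach 40. Protocol 6.1 also has an unqualified sentence requiring sub-study participation, but the neighbouring text limits it.

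**Standing and precision.** The comparison is not a listed objective, and a multi-covariate model with so few non-amplified patients will be imprecise. Both are true. They argue for one small model and modest language.

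**Conclusion.** The point holds as a gap in the analysis plan. The protocol plans a non-randomised PFS comparison by FGF status, calls the subtypes prognostically distinct and specifies no adjustment; the SAP specifies no such PFS analysis. Case mix could be mistaken for an FGF effect, or could hide one.

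The size is illustrative only: about 2 to 11 points at 6 months under the first set of assumptions, against an SE of about 9 points. A large spurious gap needs both a strong prognostic spread and a marked imbalance, and the documents establish neither. No magnitude can be given for prior lines or site mix.

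The documents do not support saying that the primary PFS estimate is biased or that the Cohort C rule would wrongly trigger. In the first range the chance of that signal stays at or below about 16%. The change should be made, but the trial's main objective does not depend on it.

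**What to change.** In SAP 12.1, with a matching line in Protocol 11.2.1:

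1. Restore the PFS comparison by FGF status in patients who started at 10 mg, keeping the protocol's rule that patients with both amplifications count as FGFR1-amplified.
2. Tabulate HR/HER2 subtype, number of prior metastatic therapies and prior anti-angiogenic therapy by FGF status.
3. Beside the unadjusted Kaplan-Meier curves, report one prespecified Cox hazard ratio with its interval, stratified by HR/HER2 subtype (SAP 8.2 categories, sparse ones merged) and adjusted for number of prior metastatic therapies (<3, 3-6, >6) and prior anti-angiogenic therapy.
4. Describe the result as associative: amplification may itself be prognostic, and SAP 8.2 records subtype at diagnosis.
5. Leave the Cohort C rule as it is, but state that it will be read alongside the balance table and the adjusted estimate.

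Repeating the model at the Cohort C sites is optional.

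The cost is SAP wording, one table and one model. Subtype and prior metastatic therapies are already SAP 8.2 variables. Prior anti-angiogenic therapy was a stratification factor before Amendment 4 and can be derived afterwards from the treatment history taken at screening (Protocol 9.1). The drawback is imprecision: there are at most about 40 non-amplified patients, and fewer at 10 mg if some entered Cohort C at 15 mg under Amendment 3.

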3.2 Targeting FGF pathway metastatic breast cancer

The gene coding for fibroblast growth factor receptor 1 (FGFR1) is amplified in roughly 10% of breast cancers [3]. Several preclinical studies have suggested that targeting FGFR1 in *FGFR1*-amplified cell lines leads to antitumor effects. Shi et al [4] have shown that dovitinib (targeting FTL3, cKIT, FGFR, vascular endothelial growth factor receptor [VEGFR] 1, VEGF2, VEGF3, platelet-derived growth factor receptor [PDGFR], and CSF1R) inhibits *FGFR1*-amplified breast cancer cell lines, but not the *FGFR* non-amplified ones. Similar results were reported in another study showing that brivanib (VEGFR and FGFR1, 2 inhibitor) inhibits FGF-induced cell proliferation in *FGFR1*-amplified cell lines [5]. Furthermore, *FGFR1*-knock down was shown to decrease cell proliferation and reverse resistance to endocrine therapy in *FGFR1*-amplified breast cancer cell lines [6]. Currently, several FGFR inhibitors are being developed in the setting of metastatic breast cancer. One phase 2 trial has reported that dovitinib demonstrated anti-tumor activity in patients with *FGFR1*-amplified, but not in *FGFR1* non-amplified breast cancers [7].

In addition to *FGFR1* amplification, approximately 15% of breast cancers demonstrate amplification of an 11q (FGF3, FGF4, Cyclin D1, or FGF19) amplicon, and this change has been associated with poor prognosis [8]. This amplicon contains genes for FGF3, FGF4, and FGF19 proteins that are ligands of FGFR1. Amplification of that chromosome region (amplicon) may lead to increased signaling in the FGF/FGFR pathway, neo-angiogenesis, and mediation of resistance to targeted and endocrine therapies [9].

3.3 Targeting angiogenesis in metastatic breast cancer

It is well established that tumor growth beyond the size of 1–2 mm is angiogenesis-dependent [10]. The VEGF plays a central role in tumor angiogenesis. The biological functions of VEGF are mediated upon binding to receptor tyrosine kinases; VEGFR-1 (FLT-1), VEGFR-2, and VEGFR-3. VEGFRs are closely related to KIT and PDGFRs and are activated upon ligand-mediated receptor dimerization [11]. VEGF-inhibitors have shown activity in patients with metastatic breast cancer [12, 13]. Nevertheless, the magnitude of treatment efficacy is low and toxicity remains significant [14]. Based on these considerations, VEGF inhibitors are not considered as standard of care, although approved and reimbursed in several countries. Recent studies have suggested that FGFR-1 could play a critical role in tumor angiogenesis and tumor growth. FGFs are potent stimulators of angiogenesis in both normal and pathological tissues, having a direct effect on both vessel assembly and sprouting [15]. Blockade of the FGF pathway can overcome resistance to VEGFR inhibitors, emphasizing the importance of FGFR and specifically the need for multi-targeted inhibitors [16, 17].

